Asthma exacerbation that requires a change in medication or worsening of asthma that requires the patient to be treated with alternative therapy will be entered into the case report form (CRF), including the date at which any medication change was made and whether this medication change was implemented prior to or after the IMPDV lung function assessments (FEV₁ and PEF) were completed. Asthma worsening including asthma exacerbations with a change to alternative asthma therapy will not be considered an adverse event for this study since it is an expected outcome for this study in an asthmatic patient population. Asthma exacerbations that meet the criteria for a serious adverse event will be recorded as adverse events.

At TV6 (week 12), or the IMPDV as applicable, the investigator will discuss asthma treatment with the patient after safety assessments have been completed, and any medication started for the purpose of newly recommended asthma treatment will not be considered a protocol violation. This asthma therapy will be recorded in the CRF following IMP discontinuation (planned or unplanned). Additionally, an investigational center visit may be conducted at any time at the request of the patient or parent/legal guardian/caregiver, as applicable or at the discretion of the investigator.

Safety will be monitored by vital signs, physical examination, oropharyngeal examination, and recording of adverse events. In addition, during the study, PEF and FEV₁ will be monitored as part of safety monitoring (alert criteria for worsening asthma). Any visual evidence of oral candidiasis during the treatment period will be confirmed by obtaining a swab for culture of the suspect area. Patients and parents/legal guardians/caregivers will be provided with guidelines for when to contact the investigational center in case of worsening asthma symptoms or rescue inhaler use. Patients who meet predefined alert criteria should be evaluated by the investigator to determine if the IMP should be discontinued. If a patient discontinues the IMP prematurely but remains in the study, all subsequent visits will include all assessments according to [Table 3](#) except for IMP dosing. Patients will be asked to perform 1-hour postdose lung function assessments at the remaining treatment visits; although the patients will not be taking a dose of IMP, the assessment should be approximately 1 hour after the predose lung function assessments were obtained.

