- ^m End of study participation in the IRT system will take place at the last visit during the treatment period (ie, at TV6 for patients who complete the treatment period, or at the IMPDV for patients who discontinue the study prematurely [patients who withdraw consent]).
- BP=blood pressure; C-ACT=Childhood Asthma Control Test; CRF=case report form; FEV₁=forced expiratory volume in 1 second; FV=follow-up visit; HFA MDI=hydrofluoroalkane metered-dose inhaler; IMP=investigational medicinal product; IMPDV=investigational medicinal product discontinuation visit; IRT=Interactive Response Technology; PEF=peak expiratory flow; RV=randomization visit; SV=screening visit; TV=treatment visit.

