4.3.1. Withdrawal for Worsening Asthma

Patients who meet the alert criteria and/or who experience a clinically meaningful worsening of their asthma will be assessed by the investigator. If the investigator considers it is not possible to safely manage a patient in a blinded manner as patient's asthma warrants a change in his/her asthma treatment, the IMP will be stopped, and appropriate treatment (based on the investigator's judgment) should be offered. The medical monitor should be contacted to confirm the findings when alternative therapy is to be instituted. The patient should continue in the study until the patient has completed all remaining study visits and the FV.

- For the purpose of this study, an asthma exacerbation is defined as worsening of asthma requiring any significant treatment other than IMP and study rescue medication. Significant treatment includes the use of systemic corticosteroids and/or the addition of other ICS-containing asthma medications, LABAs, or other NCS asthma medications, for example, inhaled short-acting muscarinic antagonist; ER/urgent care clinic visit; or hospitalization. Note: A single dose of nebulized albuterol/salbutamol would not meet the criteria for an asthma exacerbation. ER/urgent care clinic visits where the treatment is limited to a single dose of nebulized albuterol/salbutamol will not meet the criteria of an asthma exacerbation.

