4.3.2. Alert Criteria for Worsening Asthma

Alert criteria for individual patients with worsening asthma have been designed to ensure patient safety. If any of the criteria listed below are met, during scheduled or unplanned study visit, the investigator will determine whether the patient's overall clinical picture is consistent with worsening asthma and if the patient should be withdrawn from IMP (but not the study) to be placed on alternative asthma therapy in the interest of patient safety. In cases where the IMP is to be withdrawn and alternative therapy started, the investigational center staff should contact the medical monitor to confirm the findings. Meeting 1 of these alert criteria does not automatically require a patient to be withdrawn from IMP, rather it requires a clinical evaluation to determine if the patient's asthma can continue to be managed in a blinded manner per the study or necessitates a change in asthma therapy. All attempts will be made to safely continue to manage a patient in a blinded manner.

- Morning FEV₁ by handheld device measured at home falls below the FEV₁ stability limit (see Section 6.1.3) calculated at the SV for the run-in period and at baseline for the treatment period on 4 or more days (do not have to be consecutive) out of any 7-day period (7-day period is defined as any consecutive 7 days following the RV and can overlap with scheduled study investigational center visits).

- Based upon a review of patient data from the patient diary built into the handheld device, the patient has experienced any of the following during a 7-day period (7-day period is defined as any consecutive 7 days following a previous TV; 7 days can overlap with scheduled study investigational center visits):
 - 3 or more days in which 8 or more inhalations/day of rescue medication (albuterol/salbutamol HFA MDI [90 mcg ex-actuator] or equivalent) were used (any 3 days in the consecutive 7-day period)
 - 3 or more days in which the patient experienced a nighttime asthma symptom score of more than 2 (any 3 days in the consecutive 7-day period)

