Safety will be monitored by physical examination, oropharyngeal examination, vital signs, lung function assessments, and recording of adverse events. Any visual evidence of oral candidiasis during the treatment period will be confirmed by obtaining a swab for culture of the suspect area. Patients and parents/legal guardians/caregivers will be provided with guidelines for when to contact the investigational center in case of worsening asthma symptoms or rescue inhaler use. Patients who meet predefined alert criteria should be evaluated by the investigator to determine if they should be withdrawn from the study either at the next scheduled TV or an IMP discontinuation visit (IMPDV). In cases where the IMP is to be withdrawn and alternative therapy started, the investigational center staff should contact the medical monitor to confirm the findings. If a patient discontinues the study prematurely but remains in the study, all subsequent visits will include all assessments according to [Table 3](#).

– **Treatment Visits 2, 3, 4, 5, and 6 (Weeks 1, 2, 4, 8, and 12) and IMPDV**

Patients will attend the investigational center at weeks 1, 2, 4, 8, and 12. The following procedures/assessments will be performed at these visits:

- inquiry and recording of adverse events and concomitant medications
- measurements of vital signs
- perform oropharyngeal examination
- perform urine pregnancy test (for females of childbearing potential, as applicable)
- perform predose lung function assessments (FEV₁ and PEF) by handheld device

- provide training on IMP (at all but TV6 and the IMPDV) and have patient demonstrate proper technique using the provided training inhaler. The training inhaler is to be kept at the clinic and not provided to the patient to keep at home. Inhaler device training is not required for patients placed on alternative asthma therapy and who are no longer taking IMP per protocol.
- observe patient dosing with IMP
- perform 1-hour postdose lung function assessments (FEV₁ and PEF) by handheld device (morning only at TV6)
- provide handheld device training (at all but TV6)
- collect C-ACT asthma questionnaire (at TV4, TV5, TV6, and IMPDV only)
- dispense/collect rescue medication (as needed)
- dispense/collect IMP (at TV3, TV4, TV5, TV6, and the IMPDV only)
- assess alert criteria for worsening asthma
- discuss and record recommended asthma therapy (TV6 and the IMPDV only)
- end IMP in IRT system (TV6 and the IMPDV only)

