- end study participation in IRT system (IMPDV only)

16. Procedures After Investigational Medicinal Product Treatment

Patients who participate in the study in compliance with the protocol for the entire duration of the study (screening, run-in, and all TVs) will be considered to have completed the study.

a. Follow-up

For patients who complete the study or withdraw prematurely, final evaluations will be performed at the IMPDV or on the last day the patient receives the IMP, or as soon as possible thereafter. Procedures for patients who withdraw prematurely from the study are described in Section 4.3. Patients should be treated with standard of care after termination of the study as appropriate.

Patients may attend a follow-up visit one week (± 2 days) after the last TV. The follow-up visit may be in person or over the telephone. The following assessments will be performed during the follow-up visit:

- inquiry of adverse events
- inquiry of concomitant medication

The patients will be deemed to have completed the treatment period if they have completed all periods of treatment, including screening, run-in, and all treatments visits. The patient will be deemed to have completed the study period if they have completed all periods of the study, including FV in addition to screening, run-in, and all TVs. Patients who stop IMP and return for safety evaluation at week 12 will not be considered to have completed the treatment period.

Patients with ongoing adverse events will be monitored as described in Section 7.1.2. Otherwise, the follow-up visit will be the last study visit.

17. Unscheduled Visits

An unscheduled visit may be performed at any time during the study at the patient's request and as deemed necessary by the investigator. The date and reason for the unscheduled visit will be recorded on the case report form as well as any other data obtained (eg, adverse events, concomitant medications and treatments, and results from procedures or tests).

Procedures performed during unscheduled visits include the following:

- concomitant medication inquiry
- vital signs measurements
- adverse event inquiry

Other procedures may be performed at the discretion of the investigator.

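### Protocol Appendix B, Part 15 considers withdrawing an alert patient from the study, where the main text withdraws from IMP only and continues follow-up

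*Protocol*

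**What the plan says.** Appendix B, Part 15 (double-blind treatment period) covers patients who meet the predefined alert criteria. The investigator is to evaluate them to determine "if they should be withdrawn from the study either at the next scheduled TV or an IMP discontinuation visit (IMPDV". Two sentences later it adds: "If a patient discontinues the study prematurely but remains in the study", all later visits include the Table 3 assessments. The procedure list for TV2 to TV6 and the IMPDV, in the same part, ends with "end study participation in IRT system (IMPDV only".

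The main text treats the same situation differently:

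- Section 3.1: "Patients who meet predefined alert criteria should be evaluated by the investigator to determine if the IMP should be discontinued". It continues: "If a patient discontinues the IMP prematurely but remains in the study", later visits include the Table 3 assessments apart from IMP dosing.
- Section 4.3.2 has the investigator decide "if the patient should be withdrawn from IMP (but not the study) to be placed on alternative asthma therapy". The same limit, IMP and not the study, also appears in the synopsis, in Section 3.1 and in the opening of Section 7.
- Section 4.3.1, on patients whose IMP is stopped for worsening asthma: "The patient should continue in the study until the patient has completed all remaining study visits and the FV".
- Section 3.5, Table 3 footnote m closes IRT study participation at TV6 for completers, and "at the IMPDV for patients who discontinue the study prematurely [patients who withdraw consent".

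**The concern.** Appendix B is operative text. Section 3.1 says that visit procedures are detailed in Table 3 and Appendix B, and Section 3.5 points to Appendix B for by-visit detail. Neither document says that the protocol body prevails over its appendices; the SAP's precedence statement concerns differences between SAP and protocol only. A site working from Part 15 is therefore given a wrong rule for a child with worsening asthma.

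If such a child left the study, the data after IMP would be lost. Three planned outputs draw on those data:

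- the retrieved-dropout sensitivity analysis for both primary endpoints (Protocol 9.5.4.2; SAP 6.2.2.3);
- the summary of adverse events occurring more than 7 days after the last dose and before week 12, which SAP 8.4 describes as mainly for patients off IMP who continued;
- the separate concomitant-medication table for patients who stop IMP but stay (SAP 8.12).

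**Working it through.** No sample size, power or rate is involved, so the check is a comparison of current text.

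1. **Withdrawal decision.** The Appendix B sentence and its Section 3.1 counterpart open the same way. Section 3.1 asks whether the IMP should be discontinued; Appendix B asks whether the patient should leave the study. The limit to IMP and not the study stands in four places: synopsis, 3.1, 4.3.2 and 7. Section 4.3.1 implies it by requiring all remaining visits. Appendix B is the outlier.

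2. **Follow-up sentence.** A patient cannot both discontinue the study and remain in it. Section 3.1 has the same sentence with IMP in that place, and it adds the exception for IMP dosing, which Appendix B lacks. With IMP substituted, the Appendix B sentence makes sense.

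3. **Rest of Appendix B.** Part 1 counsels families that randomized patients stay unless consent is withdrawn, including those who need alternative asthma therapy. Earlier paragraphs of Part 15 instruct patients who are off IMP and still attending. The appendix as a whole therefore shares the main text's policy, and two sentences depart from it.

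4. **Intent.** The reasons recorded for Amendment 01 in Section 16.5 say that patients who discontinue IMP are still expected to attend treatment visits. That supports reading the two sentences as missed edits.

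5. **IRT line.** Table 3 marks this row at both TV6 and the IMPDV, and footnote m restricts the IMPDV case to withdrawn consent. The Appendix B line names the IMPDV alone and does not restrict the patients.

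6. **Exposure per child.** Table 3 schedules TV2, TV3, TV4, TV5 and TV6 after randomization, so at most 5 treatment visits, plus the follow-up visit, could be lost. This is a ceiling for one child, not an estimate for the trial.

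7. **Use of the data.** Protocol 9.5.4.1 imputes after IMP discontinuation whether or not retrieved data exist, so the primary result does not depend on these visits. In the sensitivity analysis, reference-based imputation applies only to patients without retrieved data. Its model is built on placebo-group data (SAP 6.2.2.3), and SAP Appendix A brings observed post-discontinuation values into that analysis. Retrieved placebo values may therefore enter the reference data, which cannot happen in the primary analysis.

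**The case against.** The strongest reply is that this is an obvious slip and that a site would be unlikely to act on it. The disputed sentence itself names an IMP discontinuation visit. The next one concerns withdrawing IMP and starting alternative therapy, and sends the site to the medical monitor. The one after that concerns patients who stay. Section 3.1 also calls for discussion with the sponsor, and the consent counselling stresses remaining in the study. All of this stands, and it makes the risk modest. It does not remove the contradiction: the paragraph still states the wrong decision.

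A second reply is that study withdrawal is not barred outright. Sections 4.3 and 7.1.8 allow it for health or safety reasons. That is correct, but those are general powers; the text specific to alerts is withdrawal from IMP only.

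Third, the IRT line has no demonstrated consequence. A reader might infer that closing IRT participation at the IMPDV stops later visits or data collection. The documents do not say so. Copying footnote m into Appendix B would also leave a gap. The protocol removes patients from the study in other ways: a broken blind (5.10.2), pregnancy (7.4.1), prohibited candidiasis therapy (7.7), and serious illness or lack of cooperation (4.3). A rule tied to withdrawn consent alone would give them no closing visit before TV6. This objection stands in full, so the IRT line is raised for consistency only.

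**Conclusion.** Two sentences in Appendix B, Part 15 contradict the main text and should be corrected. That much is certain from the wording. The consequence is a modest risk to post-IMP follow-up, and it rests on the assumption that some site applies the appendix sentence despite the surrounding text and the medical-monitor contact.

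Three stronger readings are not supported:

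- **A deliberate second policy, or children certain to be removed.** The rest of Appendix B keeps patients who are off IMP.
- **An effect on the primary analysis.** It does not use data collected after IMP discontinuation.
- **A sensitivity result drawn towards the primary result.** A reader might infer this because a child without retrieved data receives placebo-based imputation in both analyses. The method is shared, but the reference data may differ, so neither the direction nor the size of a shift can be stated.

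The documents give no basis for estimating how many children would be affected.

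**What to change.** In Appendix B, Part 15:

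1. In the alert sentence, replace *from the study* with *from IMP (but not the study)*. Leave the choice between the next scheduled TV and an IMPDV as it is, so that the timing does not change.
2. In the follow-up sentence, replace the first *the study* with *the IMP*, and after the reference to Table 3 add *except for IMP dosing*, as in Section 3.1.
3. Optional, for consistency only: change the bracket on the IRT line to *(TV6, or the IMPDV for patients who leave the study at that visit)*. Patients who stop IMP but stay are then not closed out, and patients removed for other protocol reasons are still covered.

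The cost is two wording edits, or three with the optional one. The first two restate existing policy and change no visit, assessment or analysis. The third aligns the IRT line with Table 3's TV6 entry; its wording is broader than footnote m, for the reason given above.

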APPENDIX C. QUALITY CONTROL AND QUALITY ASSURANCE

Protocol Amendments and Protocol Deviations and Violations

Protocol Amendments

No changes from the final approved (signed) protocol will be initiated without the prior written approval or favorable opinion of a written amendment by the IEC/IRB and national and local competent authorities, as applicable, except when necessary to address immediate safety concerns to the patients or when the change involves only nonsubstantial logistics or administration. The principal investigator at each investigational center, the coordinating investigator (if applicable), and the sponsor will sign the protocol amendment.

Protocol Violations

Any deviation from the protocol that affects, to a significant degree, (a) the safety, physical, or mental integrity of the patients in the study and/or (b) the scientific value of the study will be considered a protocol violation. Protocol violations may include nonadherence on the part of the patient, the investigator, or the sponsor to protocol-specific inclusion and exclusion criteria, primary objective variable criteria, or GCP guidelines; noncompliance to IMP administration; and use of prohibited medications. All protocol violations will be reported to the responsible IEC/IRB, as required.

When a protocol violation is reported, the sponsor will determine whether to discontinue the patient from the study or permit the patient to continue in the study, with documented approval from the medical expert. The decision will be based on ensuring the safety of the patient and preserving the integrity of the study.

Changes in the inclusion and exclusion criteria of the protocol are **not** prospectively granted by the sponsor. If investigational center personnel learn that a patient who did not meet protocol inclusion and exclusion criteria was entered in a study, they must immediately inform the sponsor of the protocol violation. If such patient has already completed the study or has withdrawn early, no action will be taken but the violation will be recorded.

Information to Study Personnel

The investigator is responsible for giving information about the study to all personnel members involved in the study or in any element of patient management, both before starting the study and during the course of the study (eg, when new personnel become involved). The investigator must ensure that all study personnel are qualified by education, experience, and training to perform their specific task. These study personnel members must be listed on the investigational center authorization form, which includes a clear description of each personnel member's responsibilities. This list must be updated throughout the study, as necessary.

The study monitor is responsible for explaining the protocol to all study personnel, including the investigator, and for ensuring they comply with the protocol.

Study Monitoring

To ensure compliance with GCP guidelines, the study monitor or representative is responsible for ensuring that patients have signed the informed consent form and the study is conducted according to applicable SOPs, the protocol, and other written instructions and regulatory guidelines.

The study monitor is the primary association between the sponsor and the investigator. The main responsibilities of the study monitor(s) are to visit the investigator before, during, and after the study to ensure adherence to the protocol, that all data are correctly and completely recorded and reported, and that informed consent is obtained and recorded for all patients before they participate in the study and when changes to the consent form are warranted, in accordance with IEC/IRB approvals.

The study monitor(s) will contact the investigator and visit the investigational center according to the monitoring plan. The study monitor will be permitted to review and verify the various records (CRFs and other pertinent source data records, including specific electronic source document relating to the study) to verify adherence to the protocol and to ensure the completeness, consistency, and accuracy of the data being recorded.

As part of the supervision of study progress, other sponsor personnel may, on request, accompany the study monitor on visits to the investigational center. The investigator and assisting personnel must agree to cooperate with the study monitor to resolve any problems, errors, or possible misunderstandings concerning the findings detected during the course of these monitoring visits or provided in follow-up written communication.

Audit and Inspection

The sponsor may audit the investigational center to evaluate study conduct and compliance with protocols, SOPs, GCP guidelines, and applicable regulatory requirements. The sponsor's Global Clinical Quality Assurance, independent of Global Specialty Development, is responsible for determining the need for (and timing of) an investigational center audit.

The investigator must accept that competent authorities and sponsor representatives may conduct inspections and audits to verify compliance with GCP guidelines.

